### Sensitivity analyses of the efficacy data

The following sensitivity analysis will be performed for the daily OFF time efficacy endpoint.

- MI analysis: MI techniques based on Pattern Mixture Models (PMM) will be applied ([Ratitch et al., 2011](#)) as a further sensitivity analysis in the ITT population. This methodology will structure data based on missing data patterns. The method will be based on a missingness pattern having a monotone structure, i.e. if among the observations over time one data value is missing, all other values after this missing value will also be treated as missing. For patients with intermittent missing values, before performing MI based on the PMM, it will be necessary to create a monotone missingness pattern. Intermittent missing values will be imputed using the Markov Chain Monte Carlo (MCMC) methodology which assumes a multivariate normal distribution over all variables included in the imputation model. The MI procedure in SAS will be used for this purpose and this first MI step is planned to be repeated 100 times, creating several different datasets with a monotone missing data structure. Seed value of 201508 will be used in the MI procedure. The imputation is based on the missing at random (MAR) assumption, i.e. the missing data are assumed to follow the same model as the other patients in their respective treatment group that have complete data.

After this, the remaining missing data can be imputed using a method for monotone missingness, also based on the MAR assumption. Thus, for each of the created datasets with a monotone missing data pattern, the MI procedure in SAS will be used to

## Statistical Analysis Plan

impute missing values based on a sequential procedure reflecting the monotone missing data pattern. Patients with the first missing value occurring at visit at Month 1 will have their missing Month 1 value replaced by an imputed value from a regression model with baseline value, treatment group, treatment/study group and the stratification factors as explanatory variables. In the next step, patients with their Month 3 value missing will have their missing Month 3 value replaced by an imputed value from a regression mode with baseline value, treatment group, treatment/study group and stratification factors and the Month 1 value as explanatory variables. Similar procedure will be used to replace the missing values at Month 6, 9 and 12.

The imputed datasets generated with the approach described above do contain only non-missing values and are used as input in the model for the exploratory efficacy endpoint. MMRM models similar as described above will thus be run on each of the generated imputed datasets. Finally, the MIANALYZE procedure in SAS will be applied to combine the results from these several datasets to derive an overall estimate of the within-group changes.

### Exploratory analyses of the efficacy data

- Changes from baseline in endpoints based on S&E ADL score, UPDRS Part 2 score, PHQ-9 total score, Impact of Parkinson's OFF Episodes Patient Survey score along with numeric individual score (i.e. Impact of OFF Time on Disability - ON State Disability and Impact of OFF Time on Disability - ON State Disability), and PDQ-39 sub-scores and index score. An ANCOVA model with the treatment group, treatment/study group and stratification variables as fixed factors and the baseline value as a covariate will be used to estimate the treatment group differences. In addition, the data will be presented with descriptive statistics classified by treatment group and visit. The observed cases will be used in the analysis and summaries.
- For Impact of Parkinson's OFF Episodes Patient Survey, the frequency and percentage of patients for each response will be summarized by treatment group and overall for each of the item within each section.

## Statistical Analysis Plan

### 9. SAFETY

The population used for safety analyses will be the Safety Population. The analyses are outlined below. The safety evaluation defined below includes data from all patients included in the Safety population.

For the statistical analysis of the spirometry data, the visits will be pooled as described in [Section 8](#). Otherwise, all safety data will be presented in the summaries,

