## Statistical Analysis Plan

Syndrome - Patient and Caregiver Inventory (DDS-PC), and the self-administered MDS-UPDRS Parts 1B and 2 (Movement Disorder Society -UPDRS).

- To describe the effect of CVT-301 on DLCO.
- To compare the pulmonary safety, as assessed by spirometry (FEV1, FVC and FEV1/FVC ratio) between the group of patients who were treated with CVT-301 in study [CVT 301-004](#) versus the CVT-301 patients treated with placebo in CVT 301-004.
- Change from baseline visit in UPDRS Part 4 measures of motor fluctuations (dyskinesias [Questions 32-35] and wearing off [Questions 36-39]).
- Occurrence and severity of examiner-rated dyskinesia following treatment of patients experiencing an OFF episode in the clinic.

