### 3.8. STUDY PROCEDURES AND FLOWCHART

This study has 3 periods: screening period, treatment period, and follow-up period; and a total of 9 planned visits: 2 screening visits, 6 treatment visits, and 1 follow-up visit. The maximum anticipated duration of this study for patients from the CVT-301-004 study will be approximately 59 weeks, including the final spirometry and DLCO assessment which takes place 4 to 5 weeks following the treatment period. The maximum anticipated duration of this study for CVT-301-naïve patients and CVT-301-009 patients, including the screening period and the final spirometry and DLCO assessments, will be approximately 64 weeks.

CVT-301-naïve patients (including CVT-301-005 observational arm patients) will undergo a screening period (of up to 35 days) prior to randomization. The screening period may be extended an additional 7 days if repeat screening assessments are required. The screening period will consist of 2 scheduled clinic visits: Screening Visit 1 (SV1) and Screening Visit 2 (SV2). CVT-301-004 patients will not be required to undergo the screening visits and will undergo TV1 after a 1- to 14-day period (or longer if approved by the Sponsor) following Treatment Visit 4 (TV4) of the CVT-301-004 study.

Before patients return to the clinic for TV1, they will be randomized to treatment group (see section 3.6 for details). The treatment period includes 6 separate in-clinic visits

1003804

Civitas Therapeutics, Inc.

CVT-301-004E

SAP Version 2.0

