## Statistical Analysis Plan

### Baseline

Baseline is defined as the last non-missing assessment before the first dose of CVT-301 in study CVT-301-004 for the patients who received CVT-301 in CVT-301-004 and as the last non-missing assessment before the first dose of CVT-301 in CVT-301-004E for the rest of the patients.

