### 6.4. VISIT WINDOWS

The visits recorded in database will be used for all analyses. There is no plan to re-assign visits based on actual visit dates.

For the patients who discontinue the study prematurely, a set of assessments is scheduled to be performed at the ET visit (PDQ-39, PHQ-9, PGI-C, UPDRS Part 2, UPDRS Part 4, S&E ADL score and safety assessments). The following rules will be used to analyze the data collected at the ET visit:

- For the PDQ-39, PHQ-9, PGI-C, UPDRS Part 2, UPDRS Part 4 and S&E ADL score, the data from the ET visit will be re-assigned to TV6 in case there is no TV6 assessment.

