## Statistical Analysis Plan

Table 14.3.4.2.2	Summary of Vital Signs: Actual Values and Change from Pre-dose at TV1 (Safety Population)
Table 14.3.4.2.3	Summary of Standard Vital Signs: PCS and PCSC Values by Treatment Group and Visit (Safety Population)
Table 14.3.4.2.4	Summary of Standard Vital Signs: PCS and PCSC Values by Scheduled Timepoint at TV1 (Safety Population)
Table 14.3.4.2.5	Standard Vital Signs: PCS and PCSC Values (Safety Population)
Table 14.3.4.2.6	Summary of Vital Signs: Orthostatic Hypotension by Treatment Group and Visit (Safety Population)
Table 14.3.4.2.7	Summary of Vital Signs: Orthostatic Hypotension by Scheduled Timepoint at TV1 (Safety Population)
Table 14.3.4.2.8	Orthostatic Vital Signs (Safety Population)
Table 14.3.4.3	12-Lead ECG: PCS and PCSC Criteria
Table 14.3.4.3.1	Summary of 12-Lead ECG: Actual Values and Change by Treatment Group and Visit (Safety Population)
Table 14.3.4.3.2	Summary of 12-Lead ECG: PCS and PCSC Values by Treatment Group and Visit (Safety Population)
Table 14.3.4.3.3	12-Lead Electrocardiogram (ECG): PCS and PCSC Values (All Available Population)
Table 14.3.4.4	Physical Examination by Treatment Group and Visit (Safety Population)
Table 14.3.4.5.1.1.1	Summary of Spirometry(Pulmonary Function Facility): Actual Values and Change from Baseline for FEV1 and FVC by Treatment Group and Visit (Safety Population)
Table 14.3.4.5.1.1.2	Summary of Spirometry(Pulmonary Function Facility): Actual Values and Change from Baseline for FEV1 and FVC by Treatment/Study and Visit (Safety Population)
Table 14.3.4.5.1.1.3	Summary of Spirometry (Pulmonary Function Facility): Actual Values and Change from Baseline for FEV1 by Treatment Group, Visit and Smoker Status (Safety Population)
Table 14.3.4.5.1.1.4	Summary of Spirometry (Pulmonary Function Facility): Actual Values and Change from Baseline for FEV1 by Treatment/Study, Visit and Smoker Status (Safety Population)
Table 14.3.4.5.1.2.1	Summary of Spirometry(Pulmonary Function Facility): Actual Values and Change from Baseline for FEV1 and FVC by Treatment Group and Visit Using Subset of Assessments Meeting the ATS Quality Criteria (Safety Population)
Table 14.3.4.5.1.2.2	Summary of Spirometry(Pulmonary Function Facility): Actual Values and Change from Baseline for FEV1 and FVC by Treatment/Study and Visit Using Subset of Assessments Meeting the ATS Quality Criteria (Safety Population)

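### Descriptive by-visit safety tables, as the SAP reads, give former 004 CVT-301 patients about 12 to 14 more weeks since baseline than other patients under the same visit label

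*SAP*

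**What the plan says.** **Baseline.** SAP 6.2 has two rules. "Baseline is defined as the last non-missing assessment before the first dose of CVT-301 in study CVT-301-004 for the patients who received CVT-301" in that study, and "last non-missing assessment before the first dose of CVT-301 in CVT-301-004E for the rest of the patients". The laboratory, vital-sign and ECG sections (9.5 to 9.7) repeat this.

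**Visit labels.** SAP 6.4: "The visits recorded in database will be used for all analyses. There is no plan to re-assign visits based on actual visit dates".

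**Re-timing.** For efficacy, the table in SAP 8 places former 004 CVT-301 patients by time since first CVT-301 dose. Study 004 Weeks 4 and 12 become Months 1 and 3, and 004E Months 3-9 become Months 6-12. The 004E baseline, Month 1 and Month 12 visits are not used for them. SAP 9 then says "For the statistical analysis of the spirometry data, the visits will be pooled as described in" Section 8. The next sentence, meant for all other safety data, ends at a comma in the text available to me and gives no alignment rule.

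**Tables.** The SAP 14 index lists lung-function tables both by dose and by origin, for example Table 14.3.4.5.1.1.2, "Actual Values and Change from Baseline for FEV1 and FVC by Treatment/Study and Visit (Safety Population". The by-visit laboratory, vital-sign and ECG change tables are listed by treatment group only.

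**Objective.** SAP 3.3 includes: "To compare the pulmonary safety, as assessed by spirometry (FEV1, FVC and FEV1/FVC ratio) between the group of patients" treated with CVT-301 in 004 and those given placebo there.

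**The concern.** A change from baseline is tied to the time over which it is measured. The plan moves the baseline back for one origin group, and corrects the visit label for that group in the models but not clearly in the descriptive tables. Two things follow if the tables are programmed as the text reads.

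- In the by-dose tables, a row called Month 3 or Month 12 averages two different durations and describes neither. The laboratory, vital-sign and ECG tables have no planned split by origin that would show this.
- In the treatment/study lung-function tables, the former 004 CVT-301 column covers a longer window than the naïve column. It would be expected to show more decline even with no drug effect. The report could also carry two Month 12 FEV1 changes for the same patients: one from the model, using 004E Month 9, and one from the descriptive table, using 004E Month 12.

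**Working it through.** **Inputs.** Study 004 runs 12 weeks from baseline to its last visit (SAP 8 table; I take its TV4 to be the Week 12 visit). Patients then "will undergo TV1 after a 1- to 14-day period (or longer if approved by the Sponsor" (SAP 3.8), so the gap is 1/7 = 0.14 to 2.0 weeks. 004E visits fall at Weeks 4, 12, 24, 36 and 52 (SAP 3.8). The protocol puts TV6 at 56 or 60 weeks.

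**The plan's own figure.** Section 8 moves 004E Months 3, 6 and 9 to Months 6, 9 and 12, a shift of 3 months or 12 weeks. With weeks since baseline = 12 + gap + 004E week, TV3 gives 24.1-26.0 (Month 6 = 24 weeks), TV4 gives 36.1-38.0 (Month 9 = 36) and TV5 gives 48.1-50.0 (Month 12 = 52). The shift reproduces in nominal months.

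**Weeks since baseline under one database label**

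| 004E visit | Former 004 CVT-301 | Baseline at 004E TV1 |
|---|---|---|
| TV2 | 16.1-18.0 | 4 |
| TV3 | 24.1-26.0 | 12 |
| TV4 | 36.1-38.0 | 24 |
| TV5 | 48.1-50.0 | 36 |
| TV6, SAP | 64.1-66.0 | 52 |
| TV6, protocol | 68.1-70.0 or 72.1-74.0 | 56 or 60 |

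The difference is 12.1 to 14.0 weeks in every row, and more if the sponsor approves a longer gap.

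**Pooled by-dose rows.** Mean weeks = nominal week + p × (12 + gap), where p is the share of former 004 CVT-301 patients. The documents do not give p. For assumed p = 0.2, 0.35 and 0.5, the TV3 row averages 14.4-14.8, 16.2-16.9 and 18.1-19.0 weeks, and the TV6 row (SAP) 54.4-54.8, 56.2-56.9 and 58.1-59.0.

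**Size from ageing alone.** The SAP 4.1 equation for Caucasian men gives a predicted FEV1 fall between ages 65 and 66 of 0.01303 + 2 × 0.000172 × 65.5 = 0.0356 L. Over the extra weeks this is 35.6 × 12.14/52.18 = 8.3 mL to 35.6 × 14/52.18 = 9.5 mL. At the limits of eligible age (30 and 86), the yearly falls are 0.01303 + 0.000344 × 30.5 = 0.0235 L and 0.01303 + 0.000344 × 86.5 = 0.0428 L. The full range is therefore 23.5 × 12.14/52.18 = 5.5 mL to 42.8 × 14/52.18 = 11.5 mL.

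**004 placebo patients in pulmonary-facility tables.** Protocol 11.1.7 schedules a facility test before TV1 only for naïve and 009 patients. Spirometry for 004 patients at 004E TV1 is done at the neurology site. If their facility baseline dates from 004 entry, they too have 24.1-26.0 weeks at TV3 and the offset is about 0. If it dates from 004 exit, they have 12.1-14.0 weeks, an offset of 12 for equal gaps. If a 004E TV1 value serves as baseline, the offset is 12.1-14.0.

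**The case against.** The strongest reply is that the SAP nowhere states that descriptive safety tables keep the 004E label. SAP 6.4 rules out re-assignment by actual dates, whereas Section 8 relabels by a nominal map, so the two can coexist. Section 9.1 also introduces its descriptive pulmonary summaries as analysis, so the re-timing may be meant to cover them. This stands as a real ambiguity for the lung-function tables. It does not help the laboratory, vital-sign and ECG tables, because the SAP 9 sentence is confined to spirometry.

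Stronger readings that a reader might infer are not supported:

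- **Every row sets 24-26 weeks beside 12.** Those figures belong to TV3. What is constant is the offset.
- **The FVC comparison between former 004 CVT-301 and placebo patients rests on these tables alone.** SAP 9.1 plans a model of the spirometry values by 004 treatment, although the table index lists no FVC model. The protocol's form of this objective names only FEV1 and FEV1/FVC.
- **The placebo column is known to lag by 12 to 14 weeks.** In facility tables that depends on a baseline date the documents do not give.
- **The lung-safety conclusion is biased.** The model-based comparison uses re-timed visits, and the ageing effect is small beside change categories at least 10 percentage points wide.

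**Conclusion.** The point holds as an unspecified alignment whose default reading mixes durations. Former 004 CVT-301 patients carry 12.1 to 14.0 more weeks since baseline than patients counted from 004E TV1, at every 004E visit and whichever TV6 week is used. This assumes that 004 lasted 12 weeks, that the gap was 1-14 days, and that descriptive tables follow SAP 6.4.

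It affects by-dose lung-function, laboratory, vital-sign and ECG change tables, and the side-by-side reading of the treatment/study lung-function tables. It does not affect the re-timed spirometry and DLCO models or the TEAE tables. UPDRS Part 4, AWQ and DDS-PC are worded as change from TV1 and are left out of this point. From ageing alone the distortion in FEV1 is about 8-10 mL for a man of 65. A drug effect that grows with time would add to it, but the documents give no figure for one. No time trend is given for laboratory, vital-sign or ECG values, so the size there is unknown.

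**What to change.** Complete the unfinished sentence in SAP 9 so that by-visit change-from-baseline safety summaries use nominal time since first CVT-301 dose, on the Section 8 mapping. For former 004 CVT-301 patients, show the 004E visits that Section 8 does not use in separately labelled rows, so that no safety data are dropped: TV1 (12.1-14.0 weeks), TV2 (16.1-18.0) and TV6 (64.1-66.0 on the SAP schedule). Keep listings by database visit. Where study 004 data are not available to fill the early rows, present the laboratory, vital-sign and ECG change tables by treatment/study group with time since baseline stated. State the source and date of the facility baseline for 004 placebo patients.

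On the SAP schedule the spread within a shared row falls from 12.1-14.0 weeks to at most 52 - 48.14 = 3.9 weeks. The gain in the last row is smaller if other patients' TV6 falls at the protocol's 56 weeks (56 - 50.0 = 6.0 to 56 - 48.14 = 7.9 weeks) or 60 weeks (10.0 to 11.9), so that row's label should give the actual weeks.

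The cost is SAP wording, extra rows or columns, and some table programming. The visit mapping is already needed for the models, and no new data are collected.

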#### 9.1. SPIROMETRY

For CVT-301-naïve patients and [CVT-301-009](#) patients, spirometry will be assessed at the neurology sites for screening and TV1 and the pulmonary sites will be exclusively responsible for the conduct of spirometry after TV1 (within 2 weeks prior to the 3-, 6-, 9-, and 12-month visits, and 4 to 5 weeks following completion of Treatment Visit 6 [TV6]). For patients from [CVT-301-004](#), spirometry will be assessed at the neurology sites at TV1, and the pulmonary sites will be exclusively responsible for the conduct of spirometry after TV1 as described for the CVT-301-naïve patients. Spirometry data obtained in the study site will reviewed by a central spirometry laboratory (Biomedical Systems, Inc.) which will provide a quality over read of all evaluations based on acceptability and repeatability metrics in accordance with ATS criteria. FEV1, FVC and FEV1/FVC ratio will be recorded from the single “best test” (based on effort with highest summed FEV1 and FVC). Variables will include the absolute FEV1, FVC, and FEV1/FVC ratio and FEV1 and FVC expressed as % of predicted value.

The variables from pulmonary laboratory will include the FEV1, FVC, FEV1/FVC ratio, DLCO, IVC, SVC and VA. FEV1 and FVC expressed as % of predicted value, predicted DLCO, hemoglobin (Hb) adjusted predicted DLCO, and DLCO expressed as % of these predicted values will be calculated per the method in [section 6.2](#). The following analysis will be performed:

All the parameters collected at the pulmonary laboratory as well as the % of predicted DLCO and % of Hb adjusted predicted DLCO will be summarized descriptively by treatment group and overall. In addition, the data will be summarized by treatment/study group.

- Change from baseline to other visits for each parameter.
- Number and percentage of patients with FEV1/FVC < 60% and <70% by visit
- DLCO data will also be provided to indicate whether specific determinations met American Thoracic Society (ATS) quality criteria. The proportion of DLCO/spirometry data measurements meeting or not meeting ATS quality criteria will be summarized by treatment group and overall.

## Statistical Analysis Plan

- Categories of changes (<-50%, -50% -<-40%, -40% -<-30%, , -30% -<-20%, , -20% -<-10%, -10% -<-10%, 10% -<20% , 20% -<30% , 30% -<40% , 40% -<50%, >=50%) from baseline for FEV1, FEV, FEV1/FVC ratio and DLCO by visit. The summary for FEV1 will also be provided by smoker status.

The descriptive summaries will be repeated for the subset of assessments meeting the ATS quality criteria.

Another subset analysis will be performed by excluding the DLCO data from patients with a very high intra-individual variability. For the purpose of this analysis, all patients who have a co-efficient of variation (CV) value >7.5% for FEV1 will be excluded. The CV will be calculated for each patient as standard deviation divided by the mean.

In addition to the descriptive statistics, the changes in the FEV1, FEV1/FVC ratio, and DLCO values within each treatment group and differences between the treatment groups will be estimated with MMRM. The model will include the treatment group (CVT-301 DL1 or CVT-301 DL2), treatment/study group (patients who received inhaled CVT-301 in CVT-301-004 study, patients who received placebo in CVT-301-004 study and CVT 301 naïve patients), visit (visits at 1, 3, 6, 9, and 12 months), the stratification variables (Hoehn and Yahr stage and screening FEV1 and/or FEV1/FVC) and the interaction between the treatment group and visit as fixed factors. The baseline spirometry value will be included as a covariate. An unstructured covariance structure will be applied for MMRM. In case the model will not converge with the unstructured covariance structure, the heterogeneous compound symmetry (CSH) or the heterogeneous Toeplitz structure (TOEPH) will be used instead. If the unstructured covariance structure will be used, the denominator degrees of freedom will be computed using the Kenward-Roger method. In case of other covariance structures, the BETWITHIN option will be used for the denominator degrees of freedom. The least square (LS) mean, standard error, and LS mean difference for the changes from baseline within each treatment group and overall, and between the treatment group at each visit; along with the 95% confidence interval (CI) will be provided in a table. Treatment group difference will be assessed with a 2-sided alpha level of 0.05, unless specified otherwise.

The SAS code planned for the analysis is outlined below.

```
proc mixed data=&data;
class pdsevl fevlbl trta stdygrp avisit usubjid;
model chg=base pdsevl fevlbl stdygrp avisit trta trta*avisit / ddfm=kr;
repeated avisit / subject=usubjid(trta) type=un;
lsmeans trta*avisit / cl pdiff;
ods output Diffs=DIFF_MI LSMeans=LSM_MI tests3=tests ;
run;
```

